6.3.2. Expected Duration of the Clinical Investigation and Subject Participation

Expected duration of study enrollment is 3 to 6 months. Subject participation in the study will be approximately 180 minutes.

6.3.3. Withdrawal of Subjects

Subjects must be withdrawn under the following circumstances: the subject withdraws consent, or at the discretion of investigator/study staff for subject safety and welfare.

6.3.4. Replacement of Subjects

In case a subject is withdrawn from the study, another subject may be recruited.

6.3.5. Re-contacting Subjects

If the subject fails to provide proper documentation on their individual consent form or other study documents, Masimo may re-contact the subject and ask them to return to the clinical lab in order to properly complete these documents. The subject will be re-contacted via phone or email and be asked to return as soon as possible. The subject will be compensated for travel.

6.4. Procedures

6.4.1. Schedule of Activities

The figure consists of a grid of 16 horizontal bars. The bars are composed of black and white segments. The first bar has a small black segment on the left. The second bar has a larger black segment in the center. The third bar has a small black segment on the left. The fourth bar has a large black segment in the center. The fifth bar has a small black segment on the left. The sixth bar has a large black segment in the center. The seventh bar has a small black segment on the left. The eighth bar has a large black segment in the center. The ninth bar has a small black segment on the left. The tenth bar has a large black segment in the center. The eleventh bar has a small black segment on the left. The twelfth bar has a large black segment in the center. The thirteenth bar has a small black segment on the left. The fourteenth bar has a large black segment in the center. The fifteenth bar has a small black segment on the left. The sixteenth bar has a large black segment in the center. The bars are arranged in a grid pattern, with the first five bars in the first row, the next five in the second, and the last six in the third. The bars are separated by white space, and the entire grid is set against a white background.

6.4.2. Recruitment and Prescreening

6.4.3. Consenting and Screening

Subjects must read and sign the IRB-approved informed consent document. No study related activities will be conducted until the consent form is signed.

After informed consent is obtained, subjects will be asked a brief series of health questions to ensure their eligibility for this study. Subjects who do not meet the inclusion criteria and/or meet exclusion criteria will not be eligible to participate in the study.

Clinical Performance of Masimo INVSENSOR00040

Body mass index (BMI) may also be calculated to assess for eligibility for the study.

In addition, a medical history will be recorded after the initial screening questionnaire.

An orthostatic blood pressure test is ONLY required to be performed on subjects that meet the following criteria:

The following combinations meet the criteria for performing an orthostatic blood pressure measurement. If the criteria are not met, an orthostatic blood pressure test is not required.

██████████	██████████	██████████
████	████	████
████	████	████
████	████	████
██████████	██████████	████

The orthostatic blood pressure test will start with the clinician taking the subject's blood pressure while they are lying in supine position. The subject will then stand up for 30 seconds and a second blood pressure measurement will be taken. The subject's blood pressure will need to stay above █████ to meet inclusion criteria for the study.

Female subjects will be required to take a pregnancy test. Results will be noted in study documentation. If the pregnancy test is positive, the subject will be notified and removed from the study.

6.4.4. Procedure

The subject will be seated and/or lying-in supine position and should refrain from excessive movement during the study.

If accepted into the study, the subject's vitals will be monitored with standard noninvasive monitors, including FDA-cleared pulse oximeters, ECG, and blood pressure cuff. Information from these monitors may optionally be recorded.

Transient increases in blood pressure and heart rate can be expected during line placement, needle sticks, blood draws etc. and may also be attributed to anxiety/nervousness relating to a new environment. For most participants, only the initial recorded blood pressure and/or heart rate determines a subject's qualification for the study. In the case where heart rate and blood pressure changes suggest participant discomfort or a potential safety concern, the participant will be removed from the study after qualifying, according to the discretion of medical and study staff.

Clinical Performance of Masimo INVSENSOR00040

Local anesthetics such as lidocaine or skin refrigerant (e.g. Ethyl Chloride or Pain Ease) may be used if an IV is placed, to numb the site. Subjects will be given the option to have lidocaine or numbing spray be used during IV placement for the purpose of making catheter placement more comfortable.

[REDACTED]

[REDACTED]

[REDACTED]

[REDACTED]

[REDACTED]

[REDACTED], the study device(s) will be placed on the subject's wrist. Data collection will be initiated using the automated data collection software. Sensors may be repositioned, as needed, to ensure proper placement. When the INVSENSOR00040 is placed for an extended period of time, the site should be assessed as frequently as every 1 hour. If there are any signs of loss of skin integrity and/or loss of circulation or perfusion, the device should be repositioned. The device must be removed prior to defibrillation.

Pulse oximeter output values (e.g., SpO₂, pulse rate) will be recorded using the data collection software. Raw absorbance data from the noninvasive device(s) will also be recorded using the data collection software.

Upon successful placement of the sensors and the subject's indication that they are comfortable, a baseline set of blood samples will be obtained.

A qualified person will complete blood draws. [REDACTED]

[REDACTED]

[REDACTED]

[REDACTED]

[REDACTED]

[REDACTED]

[REDACTED]

[REDACTED]

Upon indication that the subject is comfortable, a gas mixture will be administered through the mouthpiece. The gas mixture may include varying proportions of oxygen, carbon dioxide, and nitrogen. The proportion of oxygen in this mixture will be decreased in a controlled manner to lower the subject's blood oxygen saturation. The lowest targeted value will be 70% oxygen saturation. Readings near 70% will be immediately verified by the reference CO-oximeter to ensure that levels are within the targeted oxygen saturation range and to minimize time that the subject may drop below the targeted range. At any point in the study, if the subject feels uncomfortable, the subject will be given oxygen.

[REDACTED]

The timing of the blood samples will be entered into the data collection software. To allow for pulse oximeter instrument response times, the subject should be at the desired saturation level for approximately 30 seconds before and after a blood sample is taken.

The study will end at a FiO₂ equal to or greater than room air (>21%) to help the subject re-saturate after the procedures. If at any point the subject is uncomfortable with the study, the study will be stopped.

Oxygen tank pressure will be checked and noted before the study begins for subject safety purposes.

During the study, subjects may be recorded using photography and/or videography. The recordings may include sound. These

Clinical Performance of Masimo INVSENSOR00040

recordings may capture identifying features on the hand and/or arm. These recordings may be used in research, product development, product testing, training, and comparison study purposes. Subjects will be given the option to provide consent or opt-out of the recordings.

6.4.5. Ending Procedure

Study staff may take [REDACTED] to verify the subject's blood values are within normal ranges (e.g., pH, glucose, etc.).

The total overall lab time will be approximately [REDACTED]. In the event that the total lab time exceeds [REDACTED], subjects will be compensated for the extra time. Subjects will be paid according to the compensation breakdown on the consent form.

At the conclusion of the procedure, the sensor(s)/device(s), IV(s), and [REDACTED] will be removed. A set of pre-discharge vitals, such as heart rate and blood pressure, will be obtained and recorded on the case report form for subject safety purposes. Subjects will be given instructions on post care. All subjects will be instructed to contact the principal investigator or study staff in the event of any potential complication.

Subjects will be offered a snack and water or juice. Subjects are asked to consume food and/or liquid prior to leaving the clinical lab area for their safety due to study procedures such as blood removal and [REDACTED]. Subjects may also be asked to wait in the clinical lab or lobby waiting area for up to an additional 30 minutes before leaving to allow for their body to continue adjusting after the study has completed.

All subjects will be encouraged to remain in the study area until they feel fit to leave. Subjects should feel safe and able before returning to work directly after participation in the study. [REDACTED]

The subject will be allowed to leave after medical personnel determine it is safe to do so.

6.5. Monitoring plan

A separate document for the study monitoring plan will be developed and followed to ensure subject safety and GCP compliance.

7. STATISTICAL DESIGN AND ANALYSIS

7.1. Acceptance Criteria

For validation studies, acceptance criteria are determined by Masimo specifications for each design.

7.2. Sample Size

- a. Per ISO-80601, validation studies should enroll, at a minimum, at least 10 subjects and collect 200 samples across all subjects. In typical desaturation studies, the number of samples for each subject will vary depending on the subject's ability to reach and maintain the targeted SaO₂ level. [REDACTED]
- b. The final analysis will utilize statistical methods to ensure accuracy statistics are calculated with comparable density over the range 70-100 % SaO₂ and adjust for repeated measures within subjects.
- c. Depending on dropout rates, additional subjects may be enrolled to obtain sufficient representative data for factors such as gender, skin pigmentation, oxygen saturation, and other factors as required.

7.3. Statistical Analysis

a. Exclusion

The following data exclusion criteria will be applied before statistical analysis:

- i. Either reference or test device does not provide data;
- ii. Incomplete study or early termination, where the desaturation protocol could not be completed;

- iii. Reference device malfunctions and/or provides inconsistent values;
- iv. Discontinuities and abrupt dropouts due to instruments recalibration or device failure;
- v. Low signal quality, e.g. due to noise or interference.
- vi. Subject's oxygen saturation is unstable. This is determined using multiple consecutive blood draws, to be stable within 1% SaO₂ (as obtained from a reference device) to include the measurement pair.

b. Accuracy calculations

Accuracy will be reported as the Bias, Precision and A_{RMS} using the following equations:

$$\text{Bias} = \frac{1}{n} \sum_{i=1}^n (SpO_2 - SaO_2)$$

$$\text{Precision} = \sqrt{\frac{\sum_{i=1}^n (SpO_2 - SaO_2) - Bias)^2}{n}}$$

$$A_{RMS} = \sqrt{\frac{\sum_{i=1}^n (SpO_2 - SaO_2)^2}{n}}$$

The A_{RMS} and precision values will be adjusted to account for repeated measurements on each subject.

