2. IDENTIFICATION AND DESCRIPTION OF THE INVESTIGATIONAL DEVICE

2.1. Background and Study Devices

An invasive blood sample analyzed by a CO-oximeter reference instrument gives the best measure of arterial oxygen concentration as well as other blood solutes but cannot measure these parameters continuously and requires skin puncture, arterial line placement and subsequent risk of infection, hematoma, and other physiological damage.

Masimo Corporation develops non-invasive medical technologies. These devices have applications in the operating room, critical care unit, emergency room, emergency transport vehicles, alternative (home) care, as well as physicians' offices. Masimo SET, Masimo rainbow, and other newly developed Masimo technology allow real-time, non-invasive monitoring of oxygen saturation. Use of monitoring devices on patients has the potential to improve clinical outcomes while reducing the cost of care and risks to both patients and clinicians associated with arterial and venous punctures.

The investigational INVSENSOR00040 used in this study is similar to the commercially available wearable health monitoring devices except that it has a continuous SpO₂ (functional oxygen saturation) function. Masimo INVSENSOR00040 is a stand-alone wearable health monitor that combines the functionality of a pulse oximeter monitor and sensor into a single portable device that fits on a user's wrist. The device is capable of calculating SpO₂ and pulse rate (PR) [REDACTED] as well as other pulse oximeter parameters (e.g. perfusion index, etc.).

Masimo INVSENSOR00039 and/or other FDA-cleared or other commercially available pulse oximeters may be used for research purposes.

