3. JUSTIFICATION FOR THE DESIGN OF THE CLINICAL INVESTIGATION

This study is designed to compare the performance of the INVSENSOR00040 as the subjects undergo a controlled desaturation protocol. This type of study design is required to evaluate the performance of pulse oximeters based upon the ISO 80601-2-61 standard which is also adopted and referenced by the FDA.

4. BENEFITS AND RISKS OF THE INVESTIGATIONAL DEVICE, CLINICAL PROCEDURE, AND CLINICAL INVESTIGATION

4.1. Benefits:

There will be no benefit to the subject. Other possible benefits would be to society as a whole. Evaluation of the accuracy of this new device could enable users to more appropriately monitor and identify potentially life-threatening conditions.

4.2. Risks/Discomforts:

- **Device Risks:**

The noninvasive devices used in this study are similar in technology and design to some commercially available pulse oximeters and other non-invasive devices and hence have the same risks. Pulse oximeters and other non-invasive devices are commonly used and are considered to be minimal risk.

There is a small risk of temporary skin irritation or discomfort associated with exposure to the sensor, as well as potential temporary mechanical irritation or discomfort from the wrist band. There is a remote, yet possible, risk of a burn from the sensor. In the case of a sensor burn, there is the potential for permanent skin damage (scar/discoloration).

If there are any cuts and/or abrasions near the application wrist, subject will disqualified from study to avoid any discomfort.

- **Venous Cannulation Risks:**

Risks associated with venipuncture include discomfort, bruising, bleeding, swelling, infection, hematoma, decreased blood supply, damage to the blood vessel and surrounding nerves, tendons, or tissue, and loss of feeling in the hand and/or arm.

Other anticipated adverse events that may occur, include but are not limited to: vasovagal syncope (fainting), infiltrated IV, blood clot, lightheadedness, feeling flush/warm, feeling pain, feeling nauseated, throwing up, seizures, sudden drop in blood pressure/sudden increase in blood pressure, sudden drop in heart rate/sudden increase in heart rate, tingling sensation of face, arms and/or legs, sweating, and/or mouth dryness.

These anticipated adverse events are expected to be temporary.

- **Arterial Cannulation Risks:**

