6.2. Investigational device(s) and comparator(s)

The investigational INVSENSOR00040 used in this study is similar to commercially available wearable health monitoring devices except that it has a continuous SpO₂ function. The investigational INVSENSOR00040 does not pose any additional risk to patients.

Clinical Performance of Masimo INVSENSOR00040

Masimo INVSENSOR00039 and/or other FDA-cleared or other commercially available pulse oximeters may be used for research purposes.

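### The exclusion rules in 7.3a remove pairs where the wrist device gave no value, failed or had low signal quality, and no readable output shows how many, so the ARMS supports only accuracy when an acceptable reading is displayed.

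*Combined protocol and SAP*

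**What the plan says.** Section 7.3a opens: "The following data exclusion criteria will be applied before statistical analysis". Three of its six rules can act on the investigational device:

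- Rule (i): "Either reference or test device does not provide data". A missing reference and a missing test reading are treated alike.
- Rule (iv): "Discontinuities and abrupt dropouts due to instruments recalibration or device failure". It does not say which device. Rule (iii) already covers reference malfunction by name, so (iv) naturally reaches the wrist device too.
- Rule (v): "Low signal quality, e.g. due to noise or interference". It gives no threshold and no source.

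Section 7.3b continues: "Accuracy will be reported as the Bias, Precision and A_{RMS} using the following equations". The sums run over n pairs, which after 7.3a means the retained ones. The outcome measures in Section 5 are ARMS for SpO₂ against the CO-oximeter and ARMS for pulse rate (PR) against the EKG monitor. Section 2.1 says the device "is similar to the commercially available wearable health monitoring devices except that it has a continuous SpO₂" function, and Section 6.2 repeats this. The objective in Section 5 is to validate SpO₂ performance over 70-100% SaO₂ in a diverse population.

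**The concern.** A missing reference value says nothing about the device under test. A blank, dropout or failure of the wrist device at a valid, stable reference value is information about its performance. The rules merge the two and then discard both. In the readable text there is no count of attempted pairs, no tabulation of exclusions by rule or device, no limit on exclusions and no sensitivity analysis.

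Two devices with the same error when they read, one reading at nearly every blood draw and the other at half of them, would produce the same validation result. Under rules (iv) and (v) there is a further risk: a value that the device did display can be removed for a reason that lies in the device. If such values tend to be the less accurate ones, the reported ARMS is better than the ARMS over all displayed values.

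**Working it through.** The plan states no non-reading rate, exclusion rate or numeric ARMS limit in readable text, so there is no figure of its own to reproduce. Three checks follow.

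**1. Does ARMS respond to the number of lost pairs?** By the 7.3b formula, ARMS is the square root of the mean squared difference over retained pairs, so the number attempted does not enter. Section 7.2a cites a minimum of 200 samples. Taking 200 as the retained number and m as an assumed lost share, attempted pairs = 200/(1 − m), rounded up:

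| Lost share m (assumed) | Attempted pairs |
|---|---|
| 5% | 211 |
| 10% | 223 |
| 20% | 250 |
| 30% | 286 |
| 50% | 400 |

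The same ARMS is compatible with every row. The adjustment for repeated measurements in 7.3b does not alter this, because it too works on retained pairs.

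**2. What could removal do to ARMS?** ARMS over all pairs = √[(1 − m)·A² + m·B²], where A is the RMS error in kept pairs and B the RMS error in removed pairs. All inputs are assumptions. With A = 2.0% and B = 4%:

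- m = 1%: √(0.99×4 + 0.01×16) = √4.12 = 2.03
- m = 2%: √(0.98×4 + 0.02×16) = √4.24 = 2.06
- m = 10%: √(0.90×4 + 0.10×16) = √5.20 = 2.28
- m = 20%: √(0.80×4 + 0.20×16) = √6.40 = 2.53

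With B = 6%, the results at 10% and 20% are √7.20 = 2.68 and √10.40 = 3.22. In every case the study would report 2.0. If B equals A there is no shift. The shift is a real quantity only where a displayed value was removed under (iv) or (v). For a true blank there is no error to measure.

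**3. Would a count be informative at this size?** With 200 attempted pairs, treated as independent, the exact (Clopper-Pearson) 95% interval for the lost share is:

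- 0 lost: 0 to 1.8%
- 10 lost: 2.4 to 9.0%
- 20 lost: 6.2 to 15.0%
- 40 lost: 14.7 to 26.2%

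Clustering within subjects would widen these, but low and high loss would still be distinguishable.

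**The case against.** Several points on the other side stand.

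- **Leaving blanks out of ARMS is unavoidable.** The formulas need an SpO₂ minus SaO₂ difference, and a blank has none. Under rule (i) the fault is the missing count, not the removal.
- **Failures are not wholly unrecorded.** Section 14.1 counts malfunctions as device deficiencies, and Section 14.4 requires deficiencies to be recorded in the CRF and reported to the sponsor. A reader might infer that failures leave no trace anywhere, and the documents do not support that. However, nothing links this log to the performance result, and nothing says that a blank without malfunction is entered in it.
- **The low range has some protection.** Section 7.2b asks for comparable density over 70-100% SaO₂, and 7.2c allows extra subjects to fill gaps in saturation or skin pigmentation. A reader might infer that the trial can conclude nothing over 70-100%. That is too strong, since it can still support accuracy when a reading is displayed. These provisions concern the data that remain, and gaps can be filled without the loss being reported.
- **Continuous describes a function.** A reader might infer that uninterrupted availability is itself a validation target. No readable objective or outcome says so. SpO₂ accuracy is assessed at blood draws, so what is lost is measurement pairs, not every moment of wear.
- **Redaction.** Parts of the objectives, the endpoint and 7.2a are blacked out, and 7.1 places acceptance criteria in sponsor specifications. An availability measure there cannot be ruled out.
- **No evidence of direction.** That blanks or poor signals cluster at low saturation, or carry larger errors, is plausible but not documented.

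**Conclusion.** The concern holds in a limited form. Rules (i), (iv) and (v) remove test-device non-readings, failures and low-signal pairs without separating them from reference-side problems, and the readable outputs do not show how many were removed. The reported ARMS therefore supports a statement about accuracy when an acceptable reading is displayed. It does not show how often such a reading is available.

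The size is unknown because the documents give no rate. The loss could be negligible: at 1 to 2% removed with twice the error, 2.0 becomes 2.03 to 2.06. It could also matter: at 10 to 20% removed, 2.28 to 2.53. These figures rest on assumed errors and do not show that the ARMS of this trial will be biased. The change should be made because it determines what the trial can conclude. It does not invalidate the accuracy analysis itself.

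**What to change.** Split 7.3a(i), (iv) and (v) by source.

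1. **Reference-side problems:** exclude, as now.
2. **Test-device causes at a valid, stable reference value:** for SpO₂ the reference is the blood sample; for PR it is a valid EKG heart rate at the planned comparison time. Leave true blanks out of ARMS but count them.
3. **Report beside each primary ARMS:** attempted pairs, exclusions by rule, and the non-reading rate overall, per subject and by SaO₂ band (70-80, 80-90, 90-100%).
4. **Sensitivity ARMS:** restore values that were displayed but removed under (iv) or (v) for a test-device reason.
5. **Conclusion:** word it as accuracy when a reading is displayed, together with the non-reading rate.

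If a redacted section or the sponsor's specification already defines an availability measure, a cross-reference from 7.3 can serve for that part.

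The cost is SAP wording, one extra table and one sensitivity calculation. Section 6.4.4 already has device outputs and blood-sample times captured by the data collection software, so SpO₂ needs no new subjects or procedures. The planned comparison times for PR would have to be written down, and the same section makes recording from the ECG monitor optional, so the plan should confirm that EKG heart rate is recorded at those times. The downside is that a possibly unfavourable yield figure becomes visible.

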5. OBJECTIVES OF THE CLINICAL INVESTIGATION

The primary objective of this study is to:

- Validate performance of the Masimo INVSENSOR00040 functional arterial oxygen saturation (SpO₂) on a diverse subject population during no motion conditions across an arterial saturation (SaO₂) range of 70-100%, against reference arterial blood samples analyzed by a laboratory CO-oximeter reference instrument for SpO₂
- Validate performance of the Masimo INVSENSOR00040 Pulse rate (PR) within its specified range on a diverse subject population during no motion conditions while undergoing desaturations protocols, against reference Standard of care EKG monitor measuring HR.

Data using the noninvasive devices will be collected from generally healthy male and female volunteers undergoing a desaturation procedure. Study subjects of differing levels of skin pigmentation will be enrolled in the study.

This is a nonrandomized single arm study wherein all subjects are enrolled into the experimental arm and receive the INVSENSOR00040 on one wrist. Desaturation will be conducted by reducing the concentration of oxygen the study subject breathes in a controlled manner to obtain noninvasive oxygen saturation readings, SpO₂, at various levels. Reference blood samples will be repeatedly collected from the subject and analyzed using a standard laboratory CO-oximeter.

SpO₂ performance will be calculated using Accuracy root mean square (ARMS) analysis of the SpO₂ values and the reference CO-oximeter values.

PR performance will be calculated using Accuracy root mean square (ARMS) analysis of the PR values and the reference EKG monitor HR values.

Outcome Measure:

- SpO₂ Performance will be determined by calculating the ARMS value through the comparison of the noninvasive oxygen saturation measurement (SpO₂) to the arterial oxygen saturation (SaO₂) value obtained from a reference blood sample.
- PR Performance will be determined by calculating the ARMS value through the comparison of the PR to the HR values from a reference standard of care EKG monitor.

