6.1.4. Completion of the Clinical Investigation

The clinical investigation is considered complete when adequate data has been collected as per the sampling plan.

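### Do the equal-weight equations in 7.3b undo the even SaO2 coverage promised in 7.2b and leave open which ARMS is judged?

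*Combined protocol and SAP*

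**What the plan says.** Two places bear on how the SpO2 accuracy value is formed.

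- Section 7.2b: "The final analysis will utilize statistical methods to ensure accuracy statistics are calculated with comparable density over the range 70-100" % SaO2. The same sentence promises an adjustment for repeated measures within subjects.
- Section 7.3b: "Accuracy will be reported as the Bias, Precision and A_{RMS} using the following equations". Bias, precision and ARMS follow, each with divisor n and no weight or saturation band. The only adjustment added is that the ARMS and "precision values will be adjusted to account for repeated measurements on each subject".

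Section 7.3a comes before the equations: "The following data exclusion criteria will be applied before statistical analysis". Its criterion vi drops a pair unless consecutive draws are stable within 1% SaO2. Section 7.2a says that "the number of samples for each subject will vary depending on" how well the subject reaches and holds the target saturation. Section 6.1.4 ends the study when "adequate data has been collected as per the sampling plan", and 7.2c allows extra subjects so that, among other factors, oxygen saturation is adequately represented. Section 5 says SpO2 performance "will be determined by calculating the ARMS value through the comparison of the noninvasive oxygen saturation measurement" with the reference SaO2. Section 7.1 leaves acceptance to company specifications and prints no limit. Text after 7.2a and parts of 6.4 are blacked out.

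**The concern.** Read alone, 7.3b does not deliver what 7.2b promises. It repeats the repeated-measures commitment but not the density commitment. Even if the sampling plan aims for even coverage, the exclusions act after sampling. Low saturations are plausibly harder to hold steady, so criterion vi could thin that end of the range. A pooled ARMS would then give that end less weight.

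The value decides whether the device meets its specification. If error is larger where pairs are fewer, pooling flatters the device; if smaller, pooling penalises it. The sharper worry is discretion: if a pooled and a balanced value could both be called the ARMS, the more favourable could be chosen once the data are seen. A secondary worry is that the repeated-measures adjustment acts on the point value and no interval for ARMS is planned in the readable text.

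**Working it through.** The plan prints no ARMS result, limit, power or SD, so there is no figure of its own to reproduce. The check has two parts.

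**1. How far apart can the two values be?**

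From the plan: at least 25 subjects (synopsis) and 200 samples as the cited minimum (7.2a). Assumed: three bands (70-80, 80-90, 90-100% SaO2), 3 planned pairs per band per subject, zero-mean errors, and the band SDs and retention rates below. Planned pairs: 25 × 3 × 3 = 225, or 75 per band.

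Pooled ARMS = √(Σ share_b × SD_b²), where share_b is band b's share of retained pairs. Balanced ARMS = √(mean of SD_b²).

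Retention low/mid/high, with the resulting shares and pair totals:
- A, 80/90/100%: shares 0.296/0.333/0.370; 75 × 2.7 = 202.5 pairs
- B, 60/80/100%: shares 0.250/0.333/0.417; 75 × 2.4 = 180 pairs
- C, 40/70/100%: shares 0.190/0.333/0.476; 75 × 2.1 = 157.5 pairs

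Worked case, B with SDs 3/2.5/2: pooled = √(0.250×9 + 0.333×6.25 + 0.417×4) = √6.00 = 2.449. Balanced = √((9 + 6.25 + 4)/3) = √6.417 = 2.533. The difference is -3.3%.

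| Band SDs (low/mid/high) | Balanced | Pooled A | Pooled B | Pooled C |
|---|---|---|---|---|
| 3/2.5/2 | 2.533 | 2.496 (-1.5%) | 2.449 (-3.3%) | 2.388 (-5.7%) |
| 3.5/2.5/1.5 | 2.630 | 2.559 (-2.7%) | 2.466 (-6.2%) | 2.343 (-10.9%) |
| 2/2.5/3 | 2.533 | 2.569 (+1.4%) | 2.614 (+3.2%) | 2.670 (+5.4%) |
| constant | equal | equal | equal | equal |

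Even spread is sufficient for agreement but not necessary. Constant squared error also gives agreement, and so does a spread unrelated to squared error: SDs 2.5/1.5/2.5 with shares 20/33.3/46.7% give √(0.2×6.25 + 0.333×2.25 + 0.467×6.25) = 2.217, the same as the balanced value.

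For pass/fail, simulated trials used a true balanced ARMS 5% above the limit, SDs 3/2.5/2 and intraclass correlation 0.2/0.4/0.6. The two values disagreed in 8/8/6% of trials under A, 19/15/13% under B and 30/26/22% under C (2,500 trials per setting). Under A the relative standard error of the pooled ARMS was 5.9/7.5/9.4%, against the 1.5% shift.

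**2. Do the two sections conflict?**

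Section 7.2b concerns the final analysis and says statistical methods will produce the density. Section 7.3b gives the formulas. Thin the retained pairs to equal numbers per band and every share becomes 1/3; the printed formula then returns √(9/3 + 6.25/3 + 4/3) = 2.533 in expectation, the balanced value. Weighting pairs by band targets the same quantity. Both sections are then satisfied at once. Reporting only a pooled value from a markedly uneven set would not satisfy 7.2b.

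**The case for a change.** The best case for a change is that 7.2b promises an analysis step, 7.3b is where it belongs, 7.3 shows no redaction, and the step is absent. A hidden sampling plan cannot fully cure this, since pairs are removed afterwards. A systematic shift does not average out merely because it is smaller than the standard error. Naming the method would cost a sentence and no data. The 200-sample figure does not rule out heavier losses either: it speaks of samples collected, and with 5 planned pairs per band (375 in all) pattern B keeps 300 pairs and the values still disagree in 20/17/14% of trials.

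What stands is that the balancing method is unnamed and that 7.3b does not restate which ARMS is judged. It does not follow that the analyst may choose freely between pooled and balanced values, because 7.2b already ties the final statistics to the balanced one. The remaining choice is how to balance, and the concern itself would accept any stated method. Sections 6.1.4 and 7.2c also work towards coverage, and criterion ii of 7.3a may do so if it removes whole subjects who could not complete desaturation; the simulation includes none of these.

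The accompanying proposals add little. Equal weight to three 10-point bands would not even out density within a band. Replacing the promised repeated-measures adjustment is a preference: in the simulations a random-intercept version moved the pooled ARMS by a median of only 0.5-1.4%. A reported interval would be informative but would not alter pass/fail.

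**Conclusion.** No change is needed. This is a gap in detail that analysts fill sensibly. A sponsor following 7.2b and 7.3b together would report one ARMS, balanced over 70-100% SaO2 and adjusted for repeated measurements, whether by thinning or by weighting.

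The two values differ only when retained pairs are uneven, error varies with saturation, and the two are related. Under the assumed inputs the difference runs from -10.9% to +5.4%, and it is 1.4% to 2.7% in absolute size under the mildest loss pattern. These figures show sensitivity and do not predict this trial: every retention rate and SD is assumed, and the disagreement rates apply to a device placed 5% from its limit. Neither the direction nor the size here can be known from the documents. The conclusion rests on reading the 7.2b sentence as binding on the final analysis, which is its plain meaning.
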